7.3 Lost to Follow-Up

A participant will be considered lost to follow-up if she fails to return to any scheduled visits and is unable to be contacted by the study site staff.

The following actions must be taken if a participant fail to return to the clinic for any required study visit:

- The site will attempt to contact the participant and reschedule the missed visit within 30 days and counsel the participant on the importance of maintaining the assigned visit schedule and ascertain if the participant wishes to and/or should continue in the study.
- Before a participant is deemed lost to follow-up, the investigator or designee will make every effort to regain contact with the participant (where possible, 3 calls/messages and, if necessary, a certified letter to the participant's last known mailing address or local equivalent methods). These contact attempts should be documented in the participant's medical record or study file.
- Should the participant continue to be unreachable, he or she will be considered to have withdrawn from the study with a primary reason of lost to follow-up.

8. Study Assessments and Procedures

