9.2 Sample Size Determination

Based on our preliminary studies in literature (83-87), we assume an anatomic success rate in LAVR group is about 70% at 24 months. The investigators believe that a difference in success rates less than 25% will not change clinical practice, but also that the sample size should be large enough so that an observed difference in success rates of 20% would be significant; i.e., an inability to differentiate between the procedures will require an observed difference that is less than 20%.

The study will be individually randomized group-treatment trial (IRGT), which patients are randomized to surgical interventions through a common surgeon (88-90). There will be three surgeons performing each surgical treatment. The number of surgeons and patients will be the same in each clinical site. We anticipate an average of 16 individually randomized patients per surgeon in each treatment group. Outcomes for patients treated by the same surgeon tend to be more similar. We assume minimal variability, estimating a small intraclass correlation coefficient (ICC) of 0.01. The table below illustrates power to detect at least 23% difference between treatment groups with varying assumptions on ICC and dropout rates. A total of 96 patients (48 patients per group) would yield 86% power to differentiate between anatomical success rates of 70% and 93% assuming an ICC of 0.01 and a two-sided 5% level of significance. Projecting a 20% dropout/loss to follow up rate over 2 years, we anticipate recruiting and up to 120 total patients.

ICC	% Dropout	Total patients	Average patients per surgeon	Power
0.01	0	120	20	92%
	10	108	18	90%
	20	96	16	86%
0.02	0	120	20	90%
	10	108	18	87%
	20	96	16	83%
0.05	0	120	20	82%
	10	108	18	79%
	20	96	16	76%

Due to concerns that ICC is higher than expected or dropout rate is higher than 20% toward the end of 2-year follow-up, we calculated the sample size that would be needed for 87% power to differentiate between anatomical success rates of 70% and 95% (a difference of 25%) in treatment groups with a two-sided 5% level of significance. The required sample size is 39 per group, or 78 total patients.

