9.4.2 Analysis of the Primary Efficacy Endpoint(s)

Anatomical Surgical Outcome

The primary endpoint for the surgical treatment is dichotomous: success or failure at 24 months after surgery. The primary outcome measure uses the rectal compression ratio at 24 months unless there has been retreatment at an earlier time. When there is retreatment, or when the 24-month ultrasound results and POPQ results are missing and the last observed measurements were consistent with the definition of failure, then the results at 24 months will be imputed to be a failure. A sensitivity analysis will be performed to study the effect on the primary endpoint of different methods of handling dropouts and missing data. It will be conducted by assuming various values for the imputed outcomes and comparing the results under those assumptions to the results of the primary analysis.

Cochran-Mantel-Haenszel (CMH) test will be used to compare between surgical treatments adjusting for stratification factor. In addition, Generalized linear mixed-effects models (GLMMs) will be performed to yield an effect estimate of conditional on surgeon. Demographics and other characteristics at baseline (treatment group, age, BMI, menopausal status, parity, duration and severity of ODS) will be included. Surgeon will be included as a random effect to account for

correlation between outcomes of patients treated by the same surgeon. Adjusted odds ratios (ORs) will be presented with 95% confidence intervals (CIs).

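### Section 7.3 can record an unreachable woman as withdrawn 11 to 23 months before the 24-month primary ultrasound, with no instruction to try her again

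*Combined protocol and SAP*

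**What the plan says.** Section 7.3 defines loss to follow-up in one sentence: "A participant will be considered lost to follow-up if she fails to return to any scheduled visits and is unable to be contacted". The procedure that follows is tied to a single visit: "The following actions must be taken if a participant fail to return to the clinic for any required study visit". First, "The site will attempt to contact the participant and reschedule the missed visit within 30 days". Next come documented contact attempts: "where possible, 3 calls/messages and, if necessary, a certified letter to the participant's last known mailing address". If these fail, "he or she will be considered to have withdrawn from the study with a primary reason of lost to follow-up". The section gives no minimum number of missed visits, no date before which the status may not be assigned, and no instruction for the 24-month visit once it has been assigned.

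The primary endpoint in section 9.4.2 is "success or failure at 24 months after surgery", read from the compression ratio on ultrasound. If the woman was retreated earlier, or if her 24-month results are missing and her last measurements met the failure definition, the 24-month result is set to failure. For other missing results the section offers only a sensitivity analysis that tries various values, without naming them.

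Section 7.2 says that treated women who later leave the study are not replaced. Section 9.3 limits the modified intent-to-treat population to randomized women with at least one post-operative visit.

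**The concern.** After the 2-week visit the schedule is sparse: 2 months, 12 months, 24 months. A woman who is away, ill or has moved around one of the first three visits may well be reachable by month 24. A site that follows section 7.3 to the letter has closed her record by then and has no prompt to call her.

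What is at stake is the primary outcome itself. The 24-month scan can be done whether or not she attended at 12 months, so closing her out gives up a measurement that might have been obtained. Women who drop out of contact are unlikely to be a random sample of those treated, and no later analysis can recover a scan that was never taken.

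The authors do protect follow-up elsewhere: section 7.1 says that an incomplete MR examination does not end participation. Missed visits get no equivalent sentence.

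**Working it through.** **1. The plan's own figure.** Section 9.2 needs 96 evaluable patients and allows for loss: "Projecting a 20% dropout/loss to follow up rate over 2 years". Inflating, 96 / (1 − 0.20) = 120, which agrees with the plan. The projected loss is 120 − 96 = 24 women. The plan does not divide these 24 by visit or say how many could be reached again.

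**2. Time from close-out to the primary scan.** Inputs: visits at 2 weeks and 2, 12 and 24 months (section 1.1); windows of ±5, ±10 and ±10 days for the first three (section 1.3); 30 days for rescheduling (section 7.3). With a month of 365.25 / 12 = 30.44 days, 24 months is 730.5 days.

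Gap in months = (730.5 − visit day − days used before close-out) / 30.44

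| Visit missed | Visit day | No waiting | After 30 days | After late window plus 30 days |
|---|---|---|---|---|
| 2 weeks | 14 | 716.5 d = 23.5 | 686.5 d = 22.6 | 681.5 d = 22.4 |
| 2 months | 60.9 | 669.6 d = 22.0 | 639.6 d = 21.0 | 629.6 d = 20.7 |
| 12 months | 365.25 | 365.25 d = 12.0 | 335.25 d = 11.0 | 325.25 d = 10.7 |

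The fourth column is the fair one, because section 7.3 asks for the 30-day attempt first.

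**3. What sections 9.3 and 9.4.2 then assign** (absent retreatment):

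- *Closed out after missing the 2-week visit.* She has no post-operative visit, so she is outside the modified intent-to-treat population.
- *Seen at 2 weeks, closed out after missing 2 months.* She is in that population, but the schedule has no ultrasound or POP-Q at 2 weeks, so she has no post-operative measurement to carry forward.
- *Scanned at 2 months, closed out after missing 12 months.* If the 2-month ratio was above 20%, failure is imputed. If it was 20% or below, no outcome is assigned.

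**4. Whether an early success can stand in for month 24.** In the transvaginal case series described in section 4.2 (20 patients), the mean ratio was 9.2% (SD 13.7) at 2 months and 19.6% (SD 14.4) at 12 months. As a rough guide, assuming normal distributions, the share above the 20% threshold is P(Z > (20 − 9.2) / 13.7 = 0.79), about 22%, at 2 months and P(Z > (20 − 19.6) / 14.4 = 0.03), about 49%, at 12 months. That is one small series of one of the two operations, but it gives no support for reading a 24-month result from a 2-month scan.

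**5. Whether another section restores contact.** Section 4.4 only defines a completer. Section 5.5 collects contact details at consent and plans reminder calls before upcoming visits, but does not say that a woman already recorded as withdrawn still has one. Appendix E makes the study exit form available at every visit from the initial appointment on. None of these tells the site to try again.

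**The case against.** The strongest reply is that section 7.3 is not a one-strike rule. A missed visit leads to rescheduling, counselling and a check on whether the woman wishes to continue. Only someone who stays silent through calls and, if needed, a letter is closed out. This stands. A reader might infer that close-out is automatic, or that women who skip a visit because they feel well or are dissatisfied are removed. The text does not support that for anyone who answers.

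Second, section 9.4.2 uses the interim scans and earlier retreatment, so a reader who assumed that every closed-out woman has no primary outcome would be wrong. This also stands. The gap is confined to women last seen as successes or never scanned after surgery. One could argue that the pre-operative scan counts as the last observed measurement. Since entry requires a ratio above 50%, every never-scanned woman would then be a failure by rule. The section does not say this is meant.

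Third, the trial is already sized for 20% loss. That protects the number of patients, not the comparability of those who remain, and it is no reason to forgo scans that could be obtained.

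Fourth, nothing bars a woman who reappears, and sections 7.2 and 7.3 record the reason for leaving, so lost women can be told apart from those who withdrew. This is right, and no relabelling is needed. But the text gives her no route back and gives the site no duty to look for her.

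Finally, the defining sentence could be read as attending no visits at all. The procedure that leads to withdrawal starts at any one required visit, so the single-visit reading is the operative one.

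**Conclusion.** The point holds as a cheap improvement. As written, section 7.3 allows a woman who misses one interim visit and cannot be reached to be recorded as withdrawn about 11 months (12-month visit), 21 months (2-month visit) or 22.6 months (2-week visit) before the primary scan, and nothing asks the site to contact her again. These gaps assume that the full 30 days are used and that the status is assigned straight afterwards.

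A reader might infer that the gap is a year or more in every case. For the 12-month visit that is so only if the 30 days are skipped, or if the gap is counted to the end of the 24-month window.

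The number of women affected cannot be derived from the documents. It is tempting to supply one. If a third to a half of the 24 projected losses (8 to 12 women) first occurred at an interim visit and 25% to 50% of those were reachable later, 8 × 0.25 = 2 to 12 × 0.50 = 6 outcomes would be at issue. Neither fraction has a source in the plan, and the sum does not remove women to whom section 9.4.2 already assigns failure, so it should not be quoted as an estimate. The case for the change rests on its low cost and on the fact that a missed primary scan is irrecoverable.

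**What to change.** Amend section 7.3 in three respects:

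1. When a woman cannot be reached after an interim visit, record that visit as missed and keep her on the schedule.
2. Attempt contact again for the 24-month visit, using the existing steps, for every treated woman who has not withdrawn consent or been withdrawn under section 7.2, whichever earlier visits she missed.
3. Assign final lost-to-follow-up status only after the 24-month window has closed.

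Reword the defining sentence to match, so that it can no longer be read as one missed visit or as none attended. The withdrawal categories in section 7.2 can stay as they are.

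The cost is a short protocol amendment and a little coordinator time for one further round of contact, using details already collected at consent.

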8.1 Study Assessments

The surgical success or failure of will be measured by:

1. The degree of rectal hypermobility measured via dynamic pelvic ultrasound (i.e. compression ratio)

The criteria for surgical failure will be defined as follows:

1. A participant will be considered a surgical failure if:
 - b. Rectal hypermobility with compression ratio more than 20% is detected via ultrasound.
2. Otherwise, a participant will be considered a surgical "success".

In addition to dynamic pelvic ultrasound, the following assessments will be performed:

1. Postoperative pain - Participants will complete the Pain Scale (67) and an assessment of pain medication use preoperatively, and then at 2 weeks, 2, 12 and 24 months postoperatively.
2. Postoperative functional activity level – Participants will complete the Activity Assessment Scale (68) which measures functional activity preoperatively and then at 2 weeks, 2 months, 12 months, and 24 months postoperatively.
3. Global improvement in bladder function – Participants will complete the Patient Global Impression of Improvement (69) at 2, 12 and 24 months after surgery.
4. Pelvic Floor Distress Inventory (PFDI) – Prolapse and colorectal symptoms as assessed by the POPDI and CRADI (short-term) and urinary and colorectal symptoms as assessed by the UDI and CRADI (long-term) subscales. Change in symptoms from 2, 12, and 24 months will also be assessed.
5. Quality of life measured by PFIQ (65), SF-36 (70), and EQ-5D (71) at 2, 12 and 24 months. The SF-36 will also be administered to a subset of participants 2 weeks post-operatively to allow validation of the Pain and Activity Assessment Scale.
6. Pelvic muscle strength as assessed by the Brink Scale 2, 12 and 24 months.

Based on measurements above, efficacy will be defined as follows:

1. Time to anatomic recurrence (time to failure)

- a. Urinary function: compare UDI scores (65) to assess urinary function generally and Hunskaar Incontinence Severity Index to assess the presence and severity of urinary incontinence specifically. Participants will also complete the Patients Global Impression of Improvement (PGI-I) (69) for impressions of bladder function.
- b. Bowel function: compare CRADI scores (65)
- c. Prolapse symptoms: compare POPDI scores (65)

2. Non-surgical treatment for pelvic floor disorders

- a. Pessary use for prolapse
- b. Stress urinary incontinence
- c. Urge urinary incontinence and other overactive bladder symptoms
- d. Voiding dysfunction
- e. Defecating dysfunction and/or fecal incontinence

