 3. Global improvement in bladder function – Participants will complete the Patient Global Impression of Improvement (69) at 2, 12 and 24 months postoperatively.
 4. Pelvic Floor Distress Inventory (PFDI) – Prolapse and colorectal symptoms as assessed by the Pelvic Organ Prolapse Distress Inventory (POPDI) and Colorectal Anal Distress Inventory (CRADI) (short-term) and urinary and colorectal symptoms as assessed by the Urinary Distress Inventory (UDI) and CRADI (long-term) subscales at 2, 12, and 24 months postoperatively.
 5. Quality of life measured by Pelvic Floor Impact Questionnaire (PFIQ) (65), Short Form Health Survey (SF-36) (70), EuroQol-5D (EQ-5D) (71) at 2, 12 and 24 months postoperatively. The SF-36 will also be administered to a subset of participants 2 weeks post-operatively to allow validation of the Pain and Activity Assessment Scale.

6. Pelvic muscle strength measured by the Brink Scale at 2, 12, and 24 months postoperatively (72).

- Compare the use of posterior compartment dynamic pelvic ultrasound imaging versus MR defecography to measure occult rectal hypermobility.
- Develop and validate a computational finite element model and statistical shape modeling approach to describe the mechanics of normal defecation and the role of rectal and vaginal support deficiencies in causing OD symptoms.

4. Study Design

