Participants will receive the allocated transvaginal sacrospinous rectopexy surgery along with or without CVPS or laparoscopic abdominal ventral rectopexy surgery with or without CVPS as indicated for each individual and as determined before surgery (exceptions are allowed during the surgery if the surgeon decides that changing the surgical plan is in the best interest of the patient; this will be recorded as a protocol deviation). CVPS includes vaginal prolapse repair surgeries (anterior vaginal repair, posterior repair, and vault suspension) and abdominal prolapse repair surgery (sacrocolpopexy). If the participants report stress urinary incontinence at baseline, they will also receive a Tension-Free Vaginal Tape (Advantage FitTM, Boston Scientific). The primary objective of the surgical intervention is to compare the surgical success of rectal hypermobility surgery using TSR to surgery using LAVR 24 months postoperatively. The secondary objectives include comparing the change in pelvic floor disorder symptoms including OD and fecal incontinence symptoms, QOL and the incidence of perioperative and postoperative complications of these two rectal suspension procedures. We will also describe the motivations and barriers for individual women's participation in women's health research at 24 months after surgery in all participants. Data collection will occur at baseline, surgery and during hospitalization, and at 2 weeks, and 2-, 12-, and 24-months postoperatively.

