9.4.3 Analysis of the Secondary Endpoint(s)

Subjective Surgical Outcome

The secondary endpoint is the presence of OD symptoms (yes/no) at 24 months after surgery. Questionnaires that assess the presence and severity of OD symptoms include pain/activity assessment scale, global improvement in bladder function, prolapse and colorectal symptoms as assessed by POPDI, CRADI, UDI, quality of life by PFIQ, SF-36, EQ-5D, and pelvic muscle strength measured by Brink Scale. Differences between surgical treatments will be analyzed using generalized linear mixed-effects models, as described for the primary endpoint. However, imputation of missing values will not be done for secondary measures.

Validation

There will be two forms of validation: statistical and radiological. For statistical validation, we expect to see a significant and positive correlation between measurements of the Compression ratio between the two modalities. However, since the Compression ratio as measured via MR defecography is not used clinically to diagnose abnormalities in rectal support (rectal prolapse or rectal intussusception), this does not validate the use of ultrasound for diagnostic purposes. Thus, radiological validation will be performed where the Compression ratio is also correlated with a radiologist's diagnosis of an abnormality in rectal support.

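### The model for the symptom, pain and activity scores does not include each score's own screening value, and the stated change from post-operative visits cannot be carried out as written

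*Combined protocol and SAP*

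**What the plan says.** **Outcome.** Section 3 lists the PFDI subscales with their assessment times, for example "CRADI (long-term) subscales at 2, 12, and 24 months postoperatively". Section 8.1 lists the same instrument and adds "Change in symptoms from 2, 12, and 24 months will also be assessed". Its efficacy list then asks for a comparison of scores, for example "Bowel function: compare CRADI scores", without naming a visit. Section 4.1 gives as a secondary objective "comparing the change in pelvic floor disorder symptoms including OD and fecal incontinence symptoms", without a reference time and without naming the PFDI.

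**Analysis.** Section 9.4.3 defines a binary endpoint: "The secondary endpoint is the presence of OD symptoms (yes/no) at 24 months after surgery". It lists the questionnaires beneath it, then states: "Differences between surgical treatments will be analyzed using generalized linear mixed-effects models, as described for the primary endpoint". The model in 9.4.2 contains treatment arm, age, parity, BMI, menopausal status, and the duration and severity of ODS, with surgeon as a random effect. How severity of ODS is measured is not stated.

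**Available data.** The Schedule of Activities (1.3), Appendix D and Appendix E place the PFDI, Pain Scale and Activity Scale at screening as well as after surgery. The last visit is at 24 months.

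**The concern.** When a continuous score is measured before and after surgery, its own baseline is usually among the best predictors of the later value. Adjusting for it removes chance baseline imbalance from the estimate and narrows the confidence interval. The plan collects these baselines but does not name them in the model.

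The sentence in 8.1 raises a different problem. No change can be measured starting from the final visit. If the sentence is read instead as change between post-operative visits, it asks whether an early result is kept. A procedure with a stable advantage from 2 months onward would show no between-arm difference on that measure. An analyst could follow the sentence in good faith and report a quantity that does not address the secondary objective in 4.1.

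**Working it through.** **Is there a planned figure to reproduce?** No. The documents give no SD, correlation, target difference or power for any PFDI subscale, the Pain Scale or the Activity Scale.

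**Which scores have a matching baseline term?**

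| Score | Collected at screening | Matching term in 9.4.2 |
|---|---|---|
| CRADI | yes | severity of ODS, possibly and in part |
| POPDI | yes | none |
| UDI | yes | none |
| Pain Scale | yes | none |
| Activity Scale | yes | none |

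**Inputs.** From the documents: 48 evaluable women per arm (9.2) and a two-sided 5% level (9.4.1). Assumed: a true difference of 0.5 SD; a correlation r between screening and follow-up score of 0.3 to 0.7; no clustering by surgeon.

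**Variance relative to the unadjusted post-operative score**

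- Post-operative score alone: 1.
- Change from screening: 2(1 − r), which is 1.40, 1.00 and 0.60 at r = 0.3, 0.5 and 0.7.
- Post-operative score adjusted for its screening value: 1 − r², which is 0.91, 0.75 and 0.51.

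**Power.** The two-sample t test has noncentrality (0.5/√v) × √(48/2), where v is the relative variance.

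| Analysis | v | Noncentrality | Power |
|---|---|---|---|
| Post-operative score, unadjusted | 1 | 2.449 | 68% |
| Adjusted, r = 0.3 | 0.91 | 2.568 | 72% |
| Adjusted, r = 0.5 | 0.75 | 2.828 | 80% |
| Adjusted, r = 0.7 | 0.51 | 3.430 | 92% |

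A raw change score gives 54%, 68% and 88% at the same three correlations. It is worse than the plain post-operative score at r = 0.3 and no better at r = 0.5. By the normal approximation, the difference detectable with 80% power falls from 0.57 SD unadjusted to 0.55, 0.50 or 0.41 SD with adjustment.

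**Allowing for the covariate already planned.** Suppose severity of ODS correlates 0.7 with the screening score and predicts the outcome only through it. At r = 0.5 the variance is already 1 − (0.7 × 0.5)² = 0.8775. Power is then about 74% before and 81% after the screening score is added (normal approximation, which runs about one point above the t test used in the table).

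**Do the possible outcome definitions target the same quantity?** In 20,000 simulated trials (48 per arm, a 0.5 SD effect at both 2 and 24 months, correlation 0.7 between those two visits), the 24-month score, change from screening and the adjusted score all averaged a difference of 0.50 SD. The first two nevertheless disagreed on significance in about 30% to 32% of trials, because their sampling errors differ. Change from 2 to 24 months averaged zero and was significant in about 5% of trials, as expected when there is nothing to detect.

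**The case against.** Four points on the other side deserve weight.

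- **The plan does adjust for baseline.** A reader might infer that the model ignores baseline altogether. It does not: 9.4.2 includes baseline severity of ODS, which may partly serve for CRADI, the subscale closest to the trial's question. The comparison with an unadjusted 68% is therefore not a comparison with the plan, and the gains above are upper bounds. This stands.
- **The passages are not three rival definitions.** Section 3 is a schedule of assessments. Section 4.1 gives no reference time. The sentence in 8.1 says that change is assessed in addition to the scores, and may be loose wording for change at those visits. Most of this stands. What remains is one sentence that cannot be followed literally.
- **The choice between post-operative score and change from screening does not alter the target.** Under randomisation both estimate the same between-arm difference, and with the screening score in a linear model they give the identical treatment estimate. This stands. It is tempting to cite the pilot compression ratios in 4.2: 19.6 − 45.5 = −25.9 points from baseline to 12 months, but 19.6 − 9.2 = +10.4 points from 2 to 12 months. Those are within-patient means from a single-arm series of 20 women, and not PFDI data. They do not show that a comparison between arms would change sign.
- **A later SAP could add the covariate.** Section 9.4.1 defers implementation to a SAP due before database lock, and 9.4.5 summarises baseline scores by arm. The point can be settled there, but a descriptive table does not adjust an estimate, and nothing in the present text commits to the covariate.

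The variance formulas apply to continuous scores only. They do not apply to the yes/no endpoint in 9.4.3. Section 5.1 requires an affirmative answer to PFDI question 7, 8 or 14, so if symptom presence is defined by those items, every woman has the same baseline value and there is nothing to adjust for.

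**Conclusion.** The point holds for the continuous secondary scores, as a free improvement. The covariate list omits the screening value of the score being analysed; the omission is clearest for POPDI, UDI, the Pain Scale and the Activity Scale. The wording on change in 8.1 needs correction because it cannot be carried out as written, and its nearest workable reading describes durability rather than benefit.

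The size cannot be fixed from the documents. With a 0.5 SD effect, 48 per arm and no clustering, the most that adjustment could add is about 4, 12 or 24 percentage points of power at correlations of 0.3, 0.5 or 0.7 (72, 80 or 92 minus 68). Under the one illustrative assumption tried for the existing severity term, the gain at correlation 0.5 is about 7 points (81 minus 74).

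The documents do not support a claim that the plan's treatment estimate for these scores is biased: baseline imbalance under randomisation arises by chance. The primary endpoint and its sample size are unaffected.

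**What to change.** 1. In 9.4.3, for each PFDI subscale, the Pain Scale and the Activity Scale, compare the post-operative score between arms at a named visit, with the screening value of that same score added to the existing covariates.
2. Keep the binary OD-symptom endpoint as a separate item with its own definition, so that the subscale scores are not read as components of it.
3. In 8.1, reword the sentence as change from screening to 2, 12 and 24 months, or label it a separate description of durability between post-operative visits. State the same reference time in 4.1.
4. State how severity of ODS is measured.

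The cost is a few lines of text and one covariate per model. No new data are needed, since these instruments are already collected at screening. The PFIQ, SF-36, EQ-5D and Brink Scale have no screening value in the Schedule of Activities, so item 1 does not extend to them. The change should be made before outcome data are analysed.
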